In addition to the criteria for permanent discontinuation of study drug/study regimen based on CTC grade/severity (table below), permanently discontinue study drug/study regimen for the following conditions:

- Inability to reduce corticosteroid to a dose of ≤10 mg of prednisone per day (or equivalent) within 12 weeks of the start of the immune-mediated adverse event (imAE)
- Grade 3 recurrence of a previously experienced treatment-related imAE following resumption of dosing

Grade 1 No dose modification

Grade 2 Hold study drug/study regimen dose until Grade 2 resolution to Grade <1.

If toxicity worsens, then treat as Grade 3 or Grade 4.

Study drug/study regimen can be resumed once event stabilizes to Grade <1 after completion of steroid taper.

Patients with endocrinopathies who may require prolonged or continued steroid replacement can be retreated with study

drug/study regimen on the following conditions:

- 1. The event stabilizes and is controlled.
- 2. The patient is clinically stable as per Investigator or treating physician's clinical judgement.
 - 3. Doses of prednisone are at ≤ 10 mg/day or equivalent.

Toxicity Management

It is recommended that management of immune-mediated adverse events (imAEs) follows the guidelines presented in this table:

- It is possible that events with an inflammatory or immune mediated mechanism could occur in nearly all organs, some of them not noted specifically in these guidelines.
- Whether specific immune-mediated events (and/or laboratory indicators of such events) are noted in these guidelines or not, patients should be thoroughly evaluated to rule out any alternative etiology (e.g., disease progression, concomitant medications, and infections) to a possible immune-mediated event. In the absence of a clear alternative etiology, all such events should be managed as if they were immune related. General recommendations follow.
- Symptomatic and topical therapy should be considered for low-grade (Grade 1 or 2, unless otherwise specified) events.
- For persistent (>3 to 5 days) low-grade (Grade 2) or severe (Grade ≥3) events, promptly start prednisone 1 to 2 mg/kg/day PO or IV equivalent.

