- Some events with high likelihood for morbidity and/or mortality e.g., myocarditis, or other similar events even if they are not currently noted in the guidelines should progress rapidly to high dose IV corticosteroids (methylprednisolone at 2 to 4 mg/kg/day) even if the event is Grade 2, and if clinical suspicion is high and/or there has been clinical confirmation. Consider, as necessary, discussing with the study physician, and promptly pursue specialist consultation.
- If symptoms recur or worsen during corticosteroid tapering (28 days of taper), increase the corticosteroid dose (prednisone dose [e.g., up to 2 to 4 mg/kg/day PO or IV equivalent]) until stabilization or improvement of symptoms, then resume corticosteroid tapering at a slower rate (>28 days of taper).
- More potent immunosuppressives such as TNF inhibitors (e.g., infliximab; also refer to the individual sections of the imAEs for specific type of immunosuppressive) should be considered for events not responding to

Drug Substance Azacitidine/Decitabine (ASTX727)

Study Code 15-11430

Edition Number 13.0

Date 09202024

Appendix 1: Dosing Modification and Toxicity Management Guidelines for Immune-Mediated, Infusion-Related, and Non-Immune-Mediated Reactions (MEDI4736 Monotherapy or Combination Therapy With Tremelimumab or Tremelimumab Monotherapy) 17 October 2019 Version (CTCAE v4.03)

General Considerations regarding Immune-Mediated Reactions

Dose Modifications

Grade 3 Depending on the individual toxicity, study drug/study regimen may be permanently discontinued. Please refer to guidelines below.

Grade 4 Permanently discontinue study drug/study regimen.

Note: For asymptomatic amylase or lipase levels of >2.0×ULN, hold study drug/study regimen, and if complete work up shows no evidence of pancreatitis, study drug/study regimen may be continued or resumed.

Note: Study drug/study regimen should be permanently discontinued in Grade 3 events with high likelihood for morbidity and/or mortality – e.g., myocarditis, or other similar events even if they are not currently noted in the guidelines. Similarly, consider whether study drug/study regimen should be permanently discontinued in Grade 2 events with high likelihood for morbidity and/or mortality – e.g., myocarditis, or other similar events even if they are not currently noted in the guidelines – when they do not rapidly improve to Grade <1 upon treatment with systemic steroids and following full taper

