Note: There are some exceptions to permanent discontinuation of study drug for Grade 4 events (i.e., hyperthyroidism, hypothyroidism, Type 1 diabetes mellitus).

Toxicity Management

systemic steroids. Progression to use of more potent immunosuppressives should proceed more rapidly in events with high likelihood for morbidity and/or mortality – e.g., myocarditis, or other similar events even if they are not currently noted in the guidelines – when these events are not responding to systemic steroids.

- With long-term steroid and other immunosuppressive use, consider need for *Pneumocystis jirovecii* pneumonia (PJP, formerly known as *Pneumocystis carinii* pneumonia) prophylaxis, gastrointestinal protection, and glucose monitoring.
 - Discontinuation of study drug/study regimen is not mandated for Grade 3/Grade 4 inflammatory reactions attributed to local tumor response (e.g., inflammatory reaction at sites of metastatic disease and lymph nodes).
 Continuation of study drug/study regimen in this situation should be based upon a benefit-risk analysis for that patient.

AE Adverse event; CTC Common Toxicity Criteria; CTCAE Common Terminology Criteria for Adverse Events; imAE immune-mediated adverse event; IV intravenous; NCI National Cancer Institute; PO By mouth.

Pediatric Considerations regarding Immune-Mediated Reactions

Dose Modifications	Toxicity Management
The criteria for permanent discontinuation of study drug/study regimen based on CTC grade/severity is the same for pediatric patients as it is for adult patients, as	 All recommendations for specialist consultation should occur with a pediatric specialist in the specialty recommended.
well as to permanently discontinue study drug/study regimen if unable to reduce corticosteroid ≤ a dose equivalent to that required for corticosteroid replacement	 The recommendations for dosing of steroids (i.e., mg/kg/day) and for IV IG and plasmapheresis that are provided for adult patients should also be used for pediatric patients.
therapy within 12 weeks of the start of the immune-mediated event	 The infliximab 5 mg/kg IV dose recommended for adults is the same as recommended for pediatric patients ≥ 6 years old. For dosing in children younger than 6 years old, consult with a pediatric specialist.
	 For pediatric dosing of mycophenolate mofetil, consult with a pediatric specialist.

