	Grade 2	For persistent (>1 to 2 weeks) Grade 2 events, hold scheduled study drug/study regimen until resolution to Grade ≤1 or baseline. • If toxicity worsens, then treat as Grade 3. • If toxicity improves to Grade ≤1 or baseline, then resume drug/study regimen after completion of steroid taper.	For Grade 2: Obtain Dermatology consult. Consider symptomatic treatment, including oral antipruritics (e.g., diphenhydramine or hydroxyzine) and topical therapy (e.g., urea cream). Consider moderate-strength topical steroid. If no improvement of rash/skin lesions occurs within 3 to 5 days or is worsening despite symptomatic treatment and/or use of moderate strength topical steroid, consider, as necessary, discussing with study physician and promptly start systemic steroids such as prednisone 1 to 2 mg/kg/day PO or IV equivalent.

 Consider skin biopsy if the event is persistent for >1 to 2 weeks or recurs.

Grade 3 or 4

For Grade 3:

Hold study drug/study regimen until resolution to Grade ≤1 or baseline. If temporarily holding the study

drug/study regimen does not provide improvement of the Grade 3 skin rash to Grade ≤1 or baseline within 30 days, then permanently discontinue study drug/study regimen.

For Grade 4:

Permanently discontinue study drug/study regimen.

For Grade 3 or 4:

- Consult Dermatology.
- Promptly initiate empiric IV methylprednisolone 1 to 4 mg/kg/day or equivalent.
 - Consider hospitalization.
 - Monitor extent of rash [Rule of Nines].
- Consider skin biopsy (preferably more than 1) as clinically feasible.
- Once the patient is improving, gradually taper steroids over
 ≥28 days and consider prophylactic antibiotics, antifungals, and
 anti-PJP treatment (refer to current NCCN guidelines for
 treatment of cancer-related infections).^a
- Consider, as necessary, discussing with study physician.

Endocrinopathy	Any Grade	General Guidance	For Any Grade:

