(e.g., hyperthyroidism, thyroiditis, hypothyroidism, Type 1 diabetes mellitus, hypophysitis, hypophysitis, hypopituitarism, and	(depending on the type of endocrinopathy, refer to NCI CTCAE v4.03 for defining the CTC grade/severity)		 Consider consulting an endocrinologist for endocrine events. Consider, as necessary, discussing with study physician. Monitor patients for signs and symptoms of endocrinopathies. Non-specific symptoms include headache, fatigue, behavior changes, changed mental status, vertigo, abdominal pain, unusual bowel habits, polydipsia, polyuria, hypotension, and weakness. Patients should be thoroughly evaluated to rule out any
adrenal insufficiency; exocrine event of			alternative etiology (e.g., disease progression including brain metastases, or infections).

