once event stabilizes and after completion

of steroid taper.

Patients with endocrinopathies who may require prolonged or continued steroid replacement (e.g., adrenal insufficiency) can be retreated with study drug/study regimen on the following conditions:

- 1. The event stabilizes and is controlled.
- The patient is clinically stable as per investigator or treating physician's clinical judgement.
- 3. Doses of prednisone are ≤10 mg/day or equivalent.

without corticosteroids.

- Isolated Type 1 diabetes mellitus (DM) may be treated with appropriate diabetic therapy, without study drug/study regimen interruption, and without corticosteroids.
- Once patients on steroids are improving, gradually taper immunosuppressive steroids (as appropriate and with guidance of endocrinologist) over ≥28 days and consider prophylactic antibiotics, antifungals, and anti-PJP treatment (refer to current NCCN guidelines for treatment of cancer-related infections).^a
- For patients with normal endocrine workup (laboratory assessment or MRI scans), repeat laboratory assessments/MRI as clinically indicated.

Grade 3 or 4

For Grade 3 or 4 endocrinopathy other than hypothyroidism and Type 1 diabetes mellitus, hold study drug/study regimen dose until endocrinopathy symptom(s) are controlled.

Study drug/study regimen can be resumed once event stabilizes and after completion of steroid taper.

Patients with endocrinopathies who may require prolonged or continued steroid replacement (e.g., adrenal insufficiency) can be retreated with study drug/study regimen on the following conditions:

- 1. The event stabilizes and is controlled.
- The patient is clinically stable as per investigator or treating physician's clinical judgement.
- 3. Doses of prednisone are ≤10 mg/day or equivalent.

For Grade 3 or 4:

- Consult endocrinologist to guide evaluation of endocrine function and, as indicated by suspected endocrinopathy and as clinically indicated, consider pituitary scan. Hospitalization recommended.
- For all patients with abnormal endocrine work up, except those with isolated hypothyroidism or Type 1 DM, and as guided by an endocrinologist, promptly initiate empiric IV methylprednisolone 1 to 2 mg/kg/day or equivalent, as well as relevant hormone replacement (e.g., hydrocortisone, sex hormones).
- For adrenal crisis, severe dehydration, hypotension, or shock, immediately initiate IV corticosteroids with mineralocorticoid activity.

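### Appendix 1 gives incompatible stopping instructions for Grade 4 adrenal insufficiency, hypophysitis, hypopituitarism and thyroiditis

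*Combined protocol and SAP*

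**What the plan says.** The general considerations at the front of Appendix 1 set dose actions by grade:

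- **Grade 4:** "Grade 4 Permanently discontinue study drug/study regimen".
- **Grade 3:** "Depending on the individual toxicity, study drug/study regimen may be permanently discontinued. Please refer to guidelines below".
- **Exceptions to the Grade 4 line**, in a later note: "There are some exceptions to permanent discontinuation of study drug for Grade 4 events (i.e., hyperthyroidism, hypothyroidism, Type 1 diabetes mellitus").

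The endocrinopathy row, under Specific Immune-Mediated Reactions, has a wider scope than that note. Its header lists hyperthyroidism, thyroiditis, hypothyroidism, Type 1 diabetes, hypophysitis, hypopituitarism and adrenal insufficiency, plus amylase or lipase increase. Its Grade 3 or 4 entry does not separate the two grades: "For Grade 3 or 4 endocrinopathy other than hypothyroidism and Type 1 diabetes mellitus, hold study drug/study regimen dose until endocrinopathy symptom(s) are controlled". It continues: "Study drug/study regimen can be resumed once event stabilizes and after completion of steroid taper". It then gives three conditions under which patients on continuing steroid replacement may be retreated, with adrenal insufficiency as the example.

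In the body of the protocol, Section 6.4 counts any Grade 4 immune-related event as a DLT during the DLT evaluation period and removes that patient from further treatment. Section 4.3 also lists a DLT as a reason for permanent discontinuation.

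**The concern.** An investigator with a Grade 4 adrenal insufficiency or hypophysitis finds two answers in one appendix. Read from the front, the event is a permanent stop, and neither condition is among the listed exceptions. Read from the row, the event is a hold after which drug may be restarted.

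Two sites could each follow a part of Appendix 1 and handle like patients in opposite ways. What is at stake is patient safety: whether drug may be given again after a Grade 4 event.

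**Working it through.** No figure in the plan needs reproducing. The check sets the general rule and its note against the row, condition by condition, at Grade 4.

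| Condition in the row | General Grade 4 line and note | Endocrinopathy row, Grade 3 or 4 | Agree? |
|---|---|---|---|
| Hypothyroidism | Listed exception | May be treated without interruption | Yes |
| Type 1 diabetes | Listed exception | May be treated without interruption | Yes |
| Hyperthyroidism | Listed exception | Hold, may resume | Yes |
| Adrenal insufficiency | Not listed: permanent stop | Hold, may resume; named for retreatment | No |
| Hypophysitis | Not listed: permanent stop | Hold, may resume | No |
| Hypopituitarism | Not listed: permanent stop | Hold, may resume | No |
| Thyroiditis | Not listed: permanent stop | Hold, may resume | No |

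Amylase or lipase increase is left out of the comparison, because the general considerations give asymptomatic elevations their own hold-and-resume note.

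**Is there a tie-break?**

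1. The Grade 3 general line defers to the rows. The Grade 4 line next to it does not.
2. If the rows silently overrode the Grade 4 line, the note listing three exceptions would have no purpose.
3. The general considerations place endocrine retreatment on steroid replacement under Grade 2 only. The row extends the same conditions to Grade 3 or 4.
4. Section 6.5.1 sends the reader to Appendix 1 without ranking its parts. Section 4.3 refers to Section 10.3 for adverse events that require discontinuation, but Section 10.3 deals with recording and reporting and gives no such criterion for endocrine events.

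**When does it matter?** Durvalumab is given in Cycles 2 to 12, which is 12 − 2 + 1 = 11 cycles. Under Section 6.4 the DLT window closes at the end of Cycle 2, leaving Cycles 3 to 12, or 12 − 3 + 1 = 10 of the 11. If the phrase in Sections 3.1 and 11 about 28 days post Cycle 2 means one further 28-day cycle, Cycles 4 to 12 remain, or 12 − 4 + 1 = 9 of the 11. On either reading most durvalumab exposure lies outside the window. Inside it, the DLT rule removes the patient whatever the row permits.

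**How often?** The documents give no Grade 4 rate for these conditions. Table 3 in Section 1.3.1 shows 0 of 24 for hypophysitis and 0 of 24 for adrenal insufficiency. Those patients received durvalumab with a single 300 mg tremelimumab dose, and the stated minimum safety follow-up was 4 weeks. Patients now enrolled receive oral decitabine and durvalumab without tremelimumab. The table therefore gives no usable rate for this trial, and none is estimated.

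**A lesser mismatch of the same kind.** At Grade 2 the general line says "Hold study drug/study regimen dose until Grade 2 resolution to Grade <1", while the rash row says "For persistent (>1 to 2 weeks) Grade 2 events, hold scheduled study drug/study regimen until resolution to Grade ≤1 or baseline". Here too the general line does not defer to the row.

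**The case against.** The strongest defence is that the general lines are defaults and the rows are operative. The opening of the general considerations places grade-based stopping criteria in the table below. The rows for pneumonitis, colitis, nephritis, rash, neurotoxicity, neuromotor syndromes, myocarditis and myositis each restate their own Grade 4 stop, which would be needless if the general line already governed. On that view the endocrinopathy row departs on purpose. Section 6.5.1 also describes Appendix 1 as recommendations. This is a plausible account of what was intended, but the text does not state it, and it leaves the exception note without a function.

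Second, the row permits resumption and does not require it, so a site that holds and then stops permanently breaches neither passage. That stands. A reader might infer that one patient is told to be both off and on drug; the text does not go that far. The conflict is that the row allows a restart which the general line rules out.

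Third, the three listed exceptions are not the only Grade 4 relief in the appendix. Another sentence says discontinuation is not mandated for inflammatory reactions attributed to local tumor response. That is true, but it does not reach endocrine events.

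Fourth, the rash row can fairly be read as refining a default, as the rows do elsewhere: Grade 2 hypothyroidism may continue without interruption, and for Grade 2 sensory neuropathy the row only asks the investigator to consider holding. That largely stands, so rash is a secondary instance here. A reader might go on to object to the row's duration range, but similar ranges recur through the appendix, and the form of that clinical rule is for the sponsor.

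**Conclusion.** The point holds for four conditions at Grade 4: adrenal insufficiency, hypophysitis, hypopituitarism and thyroiditis. The general line and its exception note stop drug permanently, the row permits it to be resumed, and nothing ranks them. This rests on reading the note's three conditions as the complete list of endocrine exceptions, which is how it is worded, and on finding no precedence statement elsewhere in the documents.

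The practical reach is mainly Grade 4 events after the DLT window. They may be few, but the documents do not allow a count.

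A reader might infer that planned safety results become unreliable. The documents do not support that: the safety objective is stated in general terms, Section 11 assesses safety through DLTs, and no tabulation of toxicity discontinuations or dose holds is specified. The DLT rules, the biologically effective dose assessment and the sample size are unaffected. A reader might also extend the clash to amylase or lipase increase, but the separate note on asymptomatic elevations prevents that as a general claim.

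**What to change.** The sponsor should reconcile three passages of Appendix 1: the general Grade 4 line, its note of exceptions, and the endocrinopathy row for Grade 3 or 4. One added sentence in the general considerations should state which governs when a general rule and an event-specific row differ. The same sentence would settle the Grade 2 rash mismatch. Which clinical rule is right is for the sponsor to decide, and none is proposed here.

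The cost is a wording amendment to Appendix 1, with no added patients, visits or procedures and no change to the statistical section.

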10.3.1 Study recording period and follow-up for adverse events and serious adverse events

Adverse events and serious adverse events will be recorded from time of signature of informed consent, throughout the treatment period and including the follow-up period (90 days after the last dose of durvalumab (MEDI4736) + tremelimumab and 28 days after the last dose of azacitidine or oral decitabine (ASTX727)).

During the course of the study all AEs and SAEs should be proactively followed up for each subject. Every effort should be made to obtain a resolution for all events, even if the events continue after discontinuation/study completion.

If a subject discontinues from treatment for reasons other than disease progression, and therefore continues to have tumor assessments, drug or procedure-related SAEs must be captured until the patient is considered to have confirmed PD and will have no further tumor assessments.

The investigator is responsible for following all SAEs until resolution, until the subject returns to baseline status, or until the condition has stabilized with the expectation that it will remain chronic, even if this extends beyond study participation.

Drug Substance Azacitidine/Decitabine (ASTX727)

Study Code 15-11430

Edition Number 13.0

Date 09202024

Follow-up of unresolved adverse events

Any AEs that are unresolved at the subject's last visit in the study are followed up by the investigator for as long as medically indicated, but without further recording in the eCRF. After 90 days, only subjects with ongoing investigational product-related SAEs will continue to be followed for safety.

AstraZeneca/MedImmune retains the right to request additional information for any subject with ongoing AE(s)/SAE(s) at the end of the study, if judged necessary.

Post study events

After the subject has been permanently withdrawn from the study, there is no obligation for the investigator to actively report information on new AE or SAEs occurring in former study subjects after the 90-day safety follow-up period for patients treated with azacitidine or oral decitabine (ASTX727), durvalumab (MEDI4736) + tremelimumab. However, if an investigator learns of any SAEs, including death, at any time after the subject has been permanently withdrawn from study, and he/she considers there is a reasonable possibility that the event is related to study treatment, the investigator should notify the study sponsor, and AstraZeneca/MedImmune Drug Safety.

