10.3.2 Reporting of serious adverse events

All SAEs will be reported, whether or not considered causally related to the investigational product, or to the study procedure(s). The reporting period for SAEs is the period immediately following the time that study drug is administered through 90 days after the last dose of durvalumab (MEDI4736) + tremelimumab, 28 days after the last dose of azacitidine or oral decitabine (ASTX727), or until the initiation of alternative anticancer therapy. The investigator and/or Sponsor are responsible for informing the Ethics Committee and/or the Regulatory Authority of the SAE as per local requirements.

The investigator and/or sponsor must inform the FDA, via a MedWatch/AdEERs form, of any serious or unexpected adverse events that occur in accordance with the reporting obligations of 21 CFR 312.32, and will concurrently forward all such reports to AstraZeneca and ASTX Pharmaceuticals. A copy of the MedWatch/AdEERs report must be faxed to AstraZeneca and ASTX Pharmaceuticals at the time the event is reported to the FDA. It is the responsibility of the sponsor to compile all necessary information and ensure that the FDA receives a report according to the FDA reporting requirement timelines and to ensure that these reports are also submitted to AstraZeneca and ASTX Pharmaceuticals at the same time.

* A cover page should accompany the MedWatch/AdEERs form indicating the following:

Drug Substance Azacitidine/Decitabine (ASTX727)

Study Code 15-11430

Edition Number 13.0

Date 09202024

- "Notification from an Investigator Sponsored Study"
- The investigator IND number assigned by the FDA
- The investigator's name and address
- The trial name/title and AstraZeneca ISS reference number (ESR-15-11430)
- * Sponsor must also indicate, either in the SAE report or the cover page, the *causality* of events *in relation to all study medications* and if the SAE is *related to disease progression*, as determined by the principal investigator.
- * Send SAE report and accompanying cover page by way of email to AstraZeneca's designated mailbox: [contact]

If a non-serious AE becomes serious, this and other relevant follow-up information must also be provided to AstraZeneca and the FDA.

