Schedule of study procedures: follow-up for subjects who have completed azacitidine or oral decitabine (ASTX727), durvalumab (MEDI4736) and tremelimumab combination treatment and achieved disease control (until confirmed progression of disease) and subjects who have discontinued azacitidine or oral decitabine (ASTX727), durvalumab (MEDI4736), or tremelimumab due to toxicity in the absence of confirmed progression of disease

	Time Since Last Dose of Study Treatment								
Evaluation	Day (±3) Months (±1 week)							12 Months and Every 6 Months	
	30	2	3	4	6	8	10	(±2 weeks)	
Physical examination ^a	X								
Vital signs (temperature, respiratory rate, blood pressure, pulse)	X								
Weight	X								
Urine hCG or serum βhCG	X								
AE/SAE assessment	X	X	X						
Concomitant medications	X	X	X						
Palliative radiotherapy	As clinically indicated								
ECOG performance status	X	X	X		X (and month 9)			X	
Subsequent anti-cancer therapy	X	X	X	X	X	X	X	X	
Survival status: phone contact with subjects who refuse to return for evaluations and agree to be contacted		X	X	X	X	X	X	X (every 2 months)	
Hematology	X	X	X					X	
Serum chemistry	X	X	X						

Drug Substance Azacitidine/Decitabine (ASTX727)

Study Code 15-11430

Edition Number 13.0

Date 09202024

Appendix 2

Schedule of study procedures: follow-up for subjects who have completed azacitidine or oral decitabine (ASTX727), durvalumab (MEDI4736) and tremelimumab combination treatment and achieved disease control (until confirmed progression of disease) and subjects who have discontinued azacitidine or oral decitabine (ASTX727), durvalumab (MEDI4736), or tremelimumab due to toxicity in the absence of confirmed progression of disease

	Time Since Last Dose of Study Treatment										
Evaluation	Day (±3)	Mon	12 Months and Every 6 Months								
	30	2	3	4	6	8	10	(±2 weeks)			
Thyroid function tests (TSH, and fT3 and fT4) ^b	X										
Tumor biopsy	X										
Peripheral blood	X										
Tumour assessment (CT or MRI)	For subjects who achieve disease control following 12 months of treatment, tumour assessments should be performed every 12 weeks relative to the date of first infusion thereafter until confirmed PD by RECIST 1.1 by investigational site review. For subjects who discontinue MED14736 due to toxicity (or symptomatic deterioration), tumour assessments should be										

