	performed relative to the relative to the date of first infusion as follows: every 8 weeks for the first 48 weeks (per Schedule of Assessments), then every 12 weeks until confirmed PD by RECIST 1.1 by investigational site review. Please refer to Schedule of Assessments for timings of confirmatory scans.										
	Upon confirmed PD, scans should be conducted according to local standard clinical practice and submitted for central review until a new treatment is started (these scans are optional).										

a Full physical exam

Free T3 and free T4 will only be measured if TSH is abnormal. They should also be measured if there is clinical suspicion of an adverse event related to the endocrine system.

Appendix 3

Schedule of study procedures: follow-up for subjects who have discontinue azacitidine or oral decitabine (ASTX727), durvalumab (MEDI4736), and tremelimumab combination treatment due to confirmed progression of disease at the investigator discretion

	Time Since Last Dose of Study Treatment									
Evaluation	Day (±3)	Moi	nths (±	30 day	/s)		12 Months and Every 6 Months			
	30	2	3	4	6	8	10	(± 30 days)		
Physical examination ^a	X									
Vital signs (temperature, respiratory rate, blood pressure, pulse)	X									
Weight	X									
AE/SAE assessment	X		X							
Concomitant medications	X		X							
Palliative radiotherapy	As clinically indicated									
ECOG performance status ^b	X		X							
Subsequent anti-cancer therapy	X		X		X			X		
Survival status: phone contact with subjects who refuse to return for evaluations and agree to be contacted			X		X			X (every 3 months)		
Urine hCG or serum βhCG	X									
Hematology	X		X							
Serum chemistry	X		X							
Thyroid function tests (TSH, and fT3 and fT4) ^c	X									
Tumor Biopsy	X									

Appendix 3

Schedule of study procedures: follow-up for subjects who have discontinue azacitidine or oral decitabine (ASTX727), durvalumab (MEDI4736), and tremelimumab combination treatment due to confirmed progression of disease at the investigator discretion

	Time Since Last Dose of Study Treatment								
Evaluation	Day (±3) Months (± 30 days)							12 Months and Every 6 Months	
	30	2	3	4	6	8	10	(± 30 days)	
PBMCs	X								

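### After a stop for confirmed progression, the last scheduled AE/SAE check (Appendix 3, Month 3 ± 30 days) can fall about 30 days before the 90-day recording period ends

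*Combined protocol and SAP*

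**What the plan says.** **Recording period.** Section 10.3.1 has AEs and SAEs recorded from consent through treatment, "including the follow-up period (90 days after the last dose of durvalumab (MEDI4736) + tremelimumab and 28 days after the last dose of azacitidine". The 28-day term also covers oral decitabine. Sections 10.3.2 and 10.3.2.1 use the same 90 days for SAE and death reporting. Section 10.3.2 adds that SAE reporting may stop earlier, "or until the initiation of alternative anticancer therapy". Section 10.3.1 has no such cut-off.

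**Schedule after confirmed progression.** Section 8.1.3 sends these patients to Appendix 3, whose title covers those who discontinued "combination treatment due to confirmed progression of disease at the investigator discretion". Its columns are headed "Time Since Last Dose of Study Treatment". The row "AE/SAE assessment" is marked at Day 30 and Month 3 only, and the month columns read "Months (± 30 days)". Month 6 lists subsequent anti-cancer therapy and survival status, with no AE/SAE mark there or later.

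**Schedule for other patients.** Appendix 2 covers patients who complete treatment with disease control or stop for toxicity. It marks AE/SAE assessment at Day 30, Month 2 and Month 3, under the header "Day (±3) Months (±1 week)".

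**The concern.** The Month 3 visit is the only scheduled AE/SAE contact after Day 30 in Appendix 3, so it has to cover the rest of the 90-day period. With a window of 30 days on the early side, it need not reach the end of that period. Once an early visit is done, the schedule does not prompt the site to ask again. Section 13.1.2 ties the Adverse Event Report Form to the end of a treatment cycle, and no cycle is running by then. Events in the last weeks would be captured only if the patient or another clinician reported them.

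Safety of the combination is the stated secondary objective (Section 2.1.2), and Section 10.1.4 has patients monitored for immune-related events. The two appendices also differ in how closely they look for late events, and the reason for stopping decides which one applies.

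**Working it through.** This is calendar arithmetic. The plan states no derived figure to reproduce; its only figure here is the 90-day period.

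**Inputs**
- Recording period after last durvalumab: 90 days (Section 10.3.1).
- Month-column window: ±30 days (Appendix 3); ±7 days (Appendix 2).
- Last AE/SAE mark: Month 3 in both appendices.
- Durvalumab on Day 1 of each 4-week cycle (Table 9).
- Oral decitabine on Days 1-3, 1-4 or 1-5; azacitidine on Days 1-5, or Days 1-5 and 8-12 (Table 9).

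**Formulas**
- Earliest on-schedule visit = nominal Month 3 day − window.
- Gap = 90 − earliest visit, in days after the last durvalumab dose.

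**Clock starting at the last durvalumab dose**

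| Month 3 taken as | Appendix 3 earliest | Appendix 3 gap | Appendix 2 earliest | Appendix 2 gap |
|---|---|---|---|---|
| day 89 | 89 − 30 = 59 | 31 | 89 − 7 = 82 | 8 |
| day 90 | 90 − 30 = 60 | 30 | 90 − 7 = 83 | 7 |
| day 92 | 92 − 30 = 62 | 28 | 92 − 7 = 85 | 5 |

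Three calendar months last 89 to 92 days, so the Appendix 3 gap is at most 28 to 31 days and the Appendix 2 gap at most 5 to 8 days. With Month 3 at day 90, the Appendix 3 window runs from day 60 to day 120.

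**Clock starting at the last dose of any study drug.** The column heading allows this reading. Assume both drugs were given in the final cycle and take Month 3 as 90 days. The earliest visit then moves later by the days between the two last doses:
- Decitabine ending on Day 3, 4 or 5: 2, 3 or 4 days later, so the gap is 30 − 2 = 28, 27 or 26 days.
- Azacitidine ending on Day 5: 4 days later, gap 26 days.
- Azacitidine ending on Day 12: 11 days later, gap 30 − 11 = 19 days.

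The choice of clock shortens the gap but does not close it.

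**The case against.** The strongest reply is that the obligation does not depend on the visit grid. Section 10.3.1 requires recording to day 90 and proactive follow-up of all AEs and SAEs, and it asks for notification of possibly related SAEs learned of later. The window also allows visits from day 90 to day 120, which cover the whole period. All of this stands: the window is permissive and does not contradict the duty. But a day-60 visit remains fully compliant, and nothing scheduled after it asks about adverse events.

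Second, Section 4.3 refers all permanently discontinued patients to Section 10.0 and Appendix 1 or 2 for safety follow-up, whatever the reason for stopping. That could be read as applying the tighter Appendix 2 windows to progressors too. However, Appendix 1 is the toxicity management guidance, so the appendix numbers in that sentence look out of date. Section 8.1.3 and the title of Appendix 3 are specific to confirmed progression. The reference does not settle the point.

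Third, a reader might infer that a third of post-treatment events would be missed (30/90 = 33%). That requires every visit at the early limit, events spread evenly over the 90 days, and no reporting between visits. If visits were instead spread evenly over days 60 to 120 (an assumption for illustration), half would leave no gap. The mean gap would be (30 × 30 / 2) / 60 = 7.5 days, or 7.5 / 90 = about 8% of the period. The documents support neither distribution.

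Fourth, a reader might infer that event rates are biased downward in the larger group of patients. The documents give no split by reason for stopping, and Section 11 plans no comparison by it. For SAEs, the reporting duty may itself end early once new anticancer therapy starts, which is plausible after progression.

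**Conclusion.** The point holds as a minor scheduling gap. For patients who stop for confirmed progression, an on-schedule final AE/SAE assessment can precede the end of the 90-day recording period by up to about 30 days (28 to 31 with calendar months), or by about 19 to 28 days if the clock starts at the last azacitidine or decitabine dose. The corresponding limit in Appendix 2 is about a week.

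These are worst-case lengths for a visit at the early limit, not expected losses. They rest on reading Month 3 as three calendar months and on durvalumab being given on Day 1 of the final cycle. They apply only to patients who received durvalumab; those who stop during Cycle 1 have the 28-day period.

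The gap is in scheduled ascertainment. How many events would be missed, and whether rates would be biased in any group, cannot be determined from the documents. The BED determination and the DLT assessment, which ends with Cycle 2, are unaffected.

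**What to change.** Add a footnote to the Month 3 AE/SAE and concomitant-medication rows of Appendix 3, to this effect:

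*The final AE/SAE and concomitant-medication check must take place no earlier than day 90 after the last durvalumab dose (up to day 120). If the Month 3 visit occurs before day 90, complete the check by telephone at or after day 90.*

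Leave the other windows unchanged. The footnote does not forbid an earlier visit. Month 3 also carries hematology, chemistry and ECOG status, and barring assessment before day 90 could lose the only AE assessment after Day 30 in patients who then deteriorate or die. Naming durvalumab as the reference dose also removes the ambiguity about the clock.

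The cost is one footnote and one short telephone call for patients seen early. The call can be combined with the survival contact already marked at Month 3. Patients seen at or after day 90 need nothing extra.
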